1.0 Background

Patients that undergo inner ear surgery often complain of postoperative nausea and vomiting (PONV) despite prophylactic antiemetic regimens with 5HT3 antagonists, steroids and vigorous hydration. Patients still experience this unpleasant feeling that may prolong hospital stay and can lead to nutritional issues such as dehydration and huge patient and family dissatisfaction. We would like to explore the use of regional anesthesia and potential antiemetic properties and compare its efficacy to the existing therapy.

PONV is an unpleasant complication following anesthesia, it is well known that patients undergoing certain surgical procedures such as those involving the inner ear, the tympanomastoid cells, and the cochlear organ may be more prone to PONV. This complication can be anticipated in those instances and prophylactically treated with antiemetics, Vigorous hydration and cautious selection of anesthetic technique and avoidance of drugs known to promote nausea^{1,2,3}. Despite all the measures described above, vomiting still occurs often, leaving patients and their families wondering if more can be done^{4,5}.

Regional anesthesia has a therapeutic and preventive role in the incidence of PONV by reducing post-operative pain and opioids consumption.

2.0 Rationale and Specific Aim

We would like to compare the therapeutic and cost effectiveness of established therapies for postoperative nausea and vomiting to regional nerve blocks of the head and neck area an intervention known for analgesia but for which the antiemetic effects hasn't been entirely explored.

Our rationale is based on the knowledge of the anatomical innervation of the inner ear and the role of the parasympathetic nervous system in the emetic act. A lot of focus has been given on its counterpart the sympathetic nervous system and its role in painful conditions. We believe that the nerve blockade of the parasympathetic innervation can have some beneficial effect in the post-surgical patient.

The role of the vagal nerve response in the act of vomiting has been extensively studied. Observation that the Vagus nerves are predominantly sensory nerves has been shown through direct electrophysiological recordings of this afferent traffic from the vagal distribution in the GI tract to the brain stem. Vagal afferent terminals stained with horseradish peroxidase (HRP) appear to project to the dorsal motor vagal nucleus (DMVN) and to the area postrema. This latter projection may provide a visceral input for vomiting^{1,2,3}. In fact electrical stimulation of vagal afferent fibers readily evokes vomiting in experimental animals. Furthermore, stimulation of the concha of the ear which is innervated by the (sensory) auricular branch of the Vagus nerve produced activation of the solitary nucleus and its following projections: parabrachial nucleus, thalamus, amygdala, paracentral lobule, and insula shown during fMRI^{1,2,3}

This latter distribution is of interest to our study since it involves the area of surgery where the auricular branch of the vagus nerve should easily accessible for anesthetic blockade.

There shouldn't be a surprise that most of the anti-emetics in use today have a mechanism of action that involves the modulation of the vagal effect during the emetic act^{1,2,3}.

We hypothesize another potential antiemetic mechanism by the blockade of the auricular branch of the Vagus nerve at the ear canal (commonly described as nerve of Arnold) in conjunction with a block of the greater auricular nerve and lesser occipital nerve at the superficial cervical plexus level^{8,9,10}. The block would cover both the sensory innervation and of the ear canal and the inner ear. A regional anesthetic block prior to the surgical intervention on the inner ear at the superficial cervical plexus block is performed. This latter is a branch of the vagus nerve at the superficial cervical plexus (erb's point). The block would inhibit the vagal afferent to area postrema through inhibition of afferent vagal input to the medullary center.

The emetic act (vomiting) is a highly integrated physiologic reflex involving both the somatic and autonomic nervous system. We do not know how much of a relation there is between the vagal nerve branches involvement and incidence of nausea and vomiting effects are from the inner ear injury and or the inflammatory response type of response triggering the area postrema. The usual prophylactic treatment of PONV has been limited to anti-emetics such 5-HT3 and dexamethasone^{6,7}, along with aggressive fluid therapy and adequate analgesia.

We are proposing to conduct a comparative study of the therapeutic and cost effectiveness of regional anesthesia and antiemetic therapy in the prevention and treatment of PONV in children undergoing inner ear surgical procedures.

3.0 Inclusion/Exclusion

Inclusion Criteria

Patient Age 1-18 yo

Scheduled to have cochlear implantation, tympanomastoidectomy, inner ear surgery

Past history of PONV susceptibility

Exclusion Criteria

Patient/ Parents refusal

Infection at the site of local anesthetic injection

Known coagulopathy

Existing VP shunt

Severe mental disability

Any known allergic to dexamethasone (Decadron) and/or ondansetron (Zofran)

4.0 Enrollment/Randomization

Subject will be approached by [name], the surgeon at his office the day of the preoperative office visit appointment or by any member of the study team the day of the surgery in the preoperative area.

After appropriate assent and consent is obtained subject will be given an identifier and will undergo randomization using a computer program.

Subject will be assigned to either one of the three groups.

Study will involve pediatric patients Age 1-18 years old who are scheduled to undergo inner ear surgery. Subjects will be randomization into three different groups. Each group will consist of 20 patients; we intend to enroll 60 participants total.

Group A Nerve of Arnold block with superficial cervical plexus block (SCPB)

Group B IV dexamethasone (Decadron) + ondansetron (Zofran)

Group C Block + IV dexamethasone (Decadron + ondansetron (Zofran)

5.0 Study Procedures

After proper informed consent and/or assent have been obtained, all patients will receive a general anesthesia using standard of care. For all patients randomized to receive regional nerve block (Group A & C) a time out before regional anesthesia will be performed stating patient identification and proposed surgical procedure with location of the block to be performed and the medications to be injected.

Patients randomized to receive regional anesthesia will be prepared following standard universal precautions with application of sterile cleaning solution of chlorhexidine (Chloraprep) or alcohol prior to injections.

The site of local anesthetic injection will be identified according to the landmarks defined by their respective anatomical descriptions. The nerve of Arnold block is located at junction of the ear tragus and external 1/3 of ear canal which will be injected using a 30 G needle with 0.5 ml of Bupivacaine 0.25%. na

The Superficial Cervical Plexus located at Erb's Point, posterior border of the sternocleidomastoid muscle and a bisecting horizontal line drawn from the cricoid cartilage at the level of the sixth vertebrae, which is slightly posterior to the external jugular vein, this site will be injected with 3-5ml of bupivacaine 0.25% with 1:200000 of epinephrine. Surgical procedures lasting longer than 4hrs will require a repeat injection with 2.5-3 ml of bupivacaine 0.25% with 1:200000 epinephrine at this latter location after completion of the surgical procedure prior emergence from anesthesia.

Group A: to receive a homolateral (same side) to surgical site or bilateral if surgery involves both ears regional block at the Erb's point and Nerve of Arnold.

The block will be performed prior to surgical incision and may be repeated at Erb's point only with half the initial volume of local anesthetic (1.5 ml -2.5ml) at completion of surgery prior emergence from anesthesia, if the procedure lasted more than 4 hours after the initial block.

Group B: will receive an anti-emetic drug regiment comprising of dexamethasone 150mcg/kg IV (max dose of 10 mg) and ondansetron 150mc/kg IV (max single dose of 4 mg) at any time after induction of anesthesia and as soon as an intravenous line is available. If, at the anesthesiologist's discretion, ondansetron is re-dose at the end of procedure, a max total dose of 8 mg may be given.

Group C: Will receive both a homolateral or bilateral if surgery involves both ears, a regional block at Erb's point (superficial cervical plexus block) and will receive an anti-emetic drug regiment comprising of dexamethasone 150mcg/kg IV (max dose of 10 mg) and ondansetron 150mc/kg IV (max single dose of 4 mg) at any time after induction of anesthesia and as soon as an intravenous line is available. If, at the anesthesiologist's discretion, ondansetron is re-dose at the end of procedure, a max total dose of 8 mg may be given.

All three groups will receive a standardized general anesthetic regiment, prior to induction the patient *might* require an oral dose of versed 0.5mg/kg as premedication for separation anxiety. Patients will also receive induction of anesthesia either inhalational oxygen in sevoflurane or intravenous induction if subject patient has an IV access, muscle relaxants will be avoided to preserve facial nerve monitoring as required by the surgical approach. Anesthesia will be maintained with oxygen in sevoflurane or desflurane. Prior to emergence of anesthesia and at any point during the procedure, patients may receive IV analgesics (acetaminophen, morphine, fentanyl, ketamine) for postoperative analgesia according to the standard recommended pediatric dosing regiments commonly used at Riley Hospital.

All three groups will receive the standard PACU protocol for pain management and anti-nausea and vomiting intervention. Following patient's recovery starting upon emergence (t_0), all symptoms indicating nausea and/or vomiting and pain will be recorded and every 15min (t_{15}) thereafter in PACU than every 4-6 hrs. while on the inpatient unit for 24 hrs and will be treated as deemed necessary. For pain assessment a FLACC scale and Visual Analogue Scale (VAS) will be used. Complaints of, or signs or symptoms of, nausea, retching and/or vomiting will be documented in the PACU or floor for 24 hours post-operatively. For patients discharged to home prior to the 24 hours, follow up will be done by phone call using the Rhodes INRV to report post-operative nausea and vomiting.

We will also review patients chart for requests or demands for any pain medications and anti-emetics, documentation of their usage as well as times of discharge from the recovery room to the floor and their discharge from the hospital. For cost comparison and analysis we will look at itemized billing for medical services related to anesthesia, pharmacy use and IV fluid use, antiemetic interventions, medication for pain throughout hospital stay from recovery room to time of discharge from the hospital. For patients that are discharged the same day of their surgery they will be given The Rhodes INRV survey to fill out at home and will be called by phone the following day to collect that information.

A cost analysis between the three study groups taking into account all the items above will be done to compare overall cost of care between the three study groups.

6.0 Reporting of Adverse Events or Unanticipated Problems Involving Risk to Participants or Others

Risk related to the Blocks

Bleeding

Infection at the site

Intravascular local anesthetic injection

Anaphylactic/allergic reaction

Rare spread of local to deeper structures, inadvertent Phrenic nerve blockade (the injection are superficial, subcutaneous with specific landmarks)

Failure of the block to produce pain relief or to prevent nausea and vomiting

Complications related to the surgical procedure including but not limited to:

Facial nerve blockade

Risk of General Anesthesia

All precautions will be taken care of to avoid the above complications by adhering to standard of practice with strict adherence to standard ASA monitoring will be used at all time, observance of the time out procedure and surgical site marking, using universal precautions for sterility and observance of safe injection technique for the regional blocks with intermittent aspiration and injection to avoid intravascular injection and use of live imaging with ultrasound guidance if necessary.

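### The bupivacaine block is written in absolute volumes with no weight basis or maximum for ages 1 to 18, and the statements on its repeat and on Group C's block do not agree

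*Combined protocol and SAP*

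**What the plan says.** Eligibility in Section 3.0 is by age, "Patient Age 1-18 yo", with no weight criterion.

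Section 5.0 describes the block in millilitres only. The nerve of Arnold is "injected using a 30 G needle with 0.5 ml of Bupivacaine 0.25"%. At Erb's point, "this site will be injected with 3-5ml of bupivacaine 0.25% with 1:200000 of epinephrine". The Group A paragraph makes the block "bilateral if surgery involves both ears regional block at the Erb's point and Nerve of Arnold".

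The repeat is described twice in Section 5.0. The general description says that operations over 4 h "will require a repeat injection with 2.5-3 ml of bupivacaine 0.25"% with epinephrine at Erb's point. The Group A paragraph makes the repeat permissive and sets it at half the first volume, which it works out as 1.5 to 2.5 ml.

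Section 4.0 lists Group C as the block plus both antiemetics, and the general text of Section 5.0 treats Groups A and C alike. The Group C paragraph, however, names only Erb's point and does not mention a repeat.

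The other study drugs are written differently: "dexamethasone 150mcg/kg IV (max dose of 10 mg"), and ondansetron per kg with a single-dose maximum and a total if it is re-dosed. Oral premedication is also per kg, and intravenous analgesics follow the hospital's pediatric dosing.

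**The concern.** The block is the intervention under test in two of the three arms. It is the only study drug in the plan with neither a weight basis nor a maximum, in a population that runs from 1-year-olds to 18-year-olds. Two anesthesiologists who each follow the text can give different amounts to the same child, depending on which repeat sentence they use and whether they take the volumes as per side or in total.

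Two things are at stake. The first is safety: milligrams per kg rise as weight falls, and nothing in the text checks this. The second is interpretation. If Group C's paragraph is followed literally, Groups A and C differ in the block itself as well as in the antiemetics, so comparing them no longer isolates the added drugs. Exposure per kg may also vary several-fold within an arm, and the data that Section 5.0 says will be collected do not include the volume injected.

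**Working it through.** **Inputs (Section 5.0).** Bupivacaine 0.25% is 2.5 mg/ml.
- Nerve of Arnold: 0.5 ml x 2.5 = 1.25 mg.
- Erb's point: 3-5 ml x 2.5 = 7.5-12.5 mg.
- Repeat, general text: 2.5-3 ml = 6.25-7.5 mg.
- Repeat, Group A text: 1.5-2.5 ml = 3.75-6.25 mg.
- Body weight: not in the documents. I assume 8, 10, 12 and 15 kg for small children, and 60 kg for contrast.

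**The plan's own figure.** Half of 3-5 ml is 1.5-2.5 ml, so the Group A repeat volume reproduces. The general text does not follow that rule. After a 3 ml first injection, 2.5-3 ml is 83-100% of it; after 5 ml it is 50-60%. The two ranges meet only at 2.5 ml, which is half the first volume only if that volume was 5 ml.

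**Totals.** If volumes are per side, mg = sides x (plexus + Arnold + repeat) x 2.5, with the repeat counted on the sides that receive it.

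| Reading | ml | mg | mg/kg at assumed 10 kg |
|---|---|---|---|
| One side, upper volume, no repeat: 5 + 0.5 | 5.5 | 13.75 | 1.4 |
| One side, upper volume, 3 ml repeat: 5 + 0.5 + 3 | 8.5 | 21.25 | 2.1 |
| Both sides, upper volume, no repeat: 2 x 5.5 | 11 | 27.5 | 2.75 |
| Both sides, lower volume, 1.5 ml repeat each side: 2 x (3 + 0.5 + 1.5) | 10 | 25 | 2.5 |
| Both sides, lower volume, 2.5 ml repeat each side: 2 x (3 + 0.5 + 2.5) | 12 | 30 | 3.0 |
| Both sides, upper volume, 3 ml repeat on one side: 2 x 5.5 + 3 | 14 | 35 | 3.5 |
| Both sides, upper volume, 2.5 ml repeat each side: 2 x (5 + 0.5 + 2.5) | 16 | 40 | 4.0 |
| Both sides, upper volume, 3 ml repeat each side: 2 x (5 + 0.5 + 3) | 17 | 42.5 | 4.25 |
| Group C paragraph (no Arnold), both sides, general-text repeat of 3 ml each side: 2 x (5 + 3) | 16 | 40 | 4.0 |

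If the volumes are instead totals over both sides, the most that can be given is 5 + 0.5 + 3 = 8.5 ml = 21.25 mg. The per-side question alone therefore changes the upper bound two-fold.

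**By weight.** 42.5 mg is 5.3 mg/kg at 8 kg, 4.25 at 10, 3.5 at 12, 2.8 at 15 and 0.7 at 60. For one side without a repeat, 13.75 mg is 1.7, 1.4, 1.1 and 0.9 mg/kg at 8, 10, 12 and 15 kg.

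**Can choice within 3-5 ml absorb the weight range?** The per-side total runs from 3.5 to 5.5 ml, a ratio of 1.57. Assumed weights of 10 and 60 kg have a ratio of 6. With the smallest volume at 10 kg (8.75/10 = 0.875 mg/kg) and the largest at 60 kg (13.75/60 = 0.23 mg/kg), a 3.8-fold difference remains.

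**The case against.** The strongest reply is that the high totals need every upper limit at once: both ears operated on, 5 ml per side, surgery over 4 h, the larger of the two repeat volumes, and that repeat on both sides, which the text does not state. The total is also spread over two administrations more than 4 h apart and takes no account of clearance. This stands. The 42.5 mg is an upper bound on one reading, not a typical dose, and a one-sided block without a repeat is far below it.

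A reader might infer that the plan permits 4.25 mg/kg as its maximum. It does not say so. That figure needs a 10 kg child, and a lighter child would exceed it. A reader might also infer that a safe limit is breached. The documents state no limit, so they cannot show a breach. Nor do they show that all 40 children in Groups A and C are affected: the arithmetic bears mainly on light children with bilateral, long operations, and no distribution of weight, laterality or duration is given.

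It is fair to add that 3-5 ml is a range that leaves room for judgement, and that Section 6.0 promises accepted practice, monitoring and careful injection technique. But no rule ties the choice within the range to weight, and Section 6.0 gives no dose figure. Its list of block risks names intravascular injection but not total dose.

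**Conclusion.** The point holds as a defect of specification in the experimental intervention. Three things rest on the text alone: the block has no weight basis or maximum while the antiemetics have both; the two repeat statements disagree on volume and on whether the repeat is required; and Group C's paragraph does not match Section 4.0 or the general procedure.

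The size depends on the reading. The upper bound is 42.5 mg if volumes are per side and the repeat is bilateral, 35 mg if the repeat is on one side, and 21.25 mg if volumes are totals. Every mg/kg figure rests on an assumed weight. The conclusion is that the written plan does not determine a child's exposure; it is not that a particular dose is unsafe.

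**What to change.** In Section 5.0:
- Reconcile the two repeat statements, on volume and on mandatory versus optional.
- State whether block volumes are per side or in total, and whether the repeat is bilateral.
- Reconcile the Group C paragraph with Section 4.0 and with the general block description, including the nerve of Arnold and the repeat.
- Have the sponsor reconcile the unscaled volumes with the age range in Section 3.0 and with the per-kg, capped way in which the antiemetics are written. Whether a limit applies, and what it is, is for the sponsor and pharmacy; none is proposed here.
- Record total ml and mg/kg of bupivacaine for each child in Groups A and C, so that exposure can be described by arm.

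The cost is protocol wording and one case-report field. The design and sample size do not change.

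### Section 5.0 gives two conflicting rules for the repeat Erb's point injection in operations over 4 hours: mandatory at 2.5–3 ml, or optional at half the initial volume (1.5–2.5 ml)

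*Combined protocol and SAP*

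**What the plan says.** All the relevant text is in Section 5.0 (Study Procedures) of the combined protocol and SAP.

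- **Who gets the block.** The general block text opens with "For all patients randomized to receive regional nerve block (Group A & C" and so covers both block arms.
- **Initial volume at Erb's point.** "this site will be injected with 3-5ml of bupivacaine 0.25% with 1:200000 of epinephrine".
- **Repeat, general block text.** "Surgical procedures lasting longer than 4hrs will require a repeat injection with 2.5-3 ml of bupivacaine 0.25% with 1:200000 epinephrine". The site is Erb's point, and the injection is given after surgery ends and before the child wakes.
- **Repeat, Group A paragraph.** The block "may be repeated at Erb's point only with half the initial volume of local anesthetic (1.5 ml -2.5ml", at the same site and the same moment, "if the procedure lasted more than 4 hours after the initial block".
- **Group C paragraph.** It provides "a regional block at Erb's point (superficial cervical plexus block) and will receive an anti-emetic drug regiment" and states no repeat rule of its own.

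Section 4.0 sets the numbers: "Each group will consist of 20 patients; we intend to enroll 60 participants total".

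**The concern.** The two repeat rules describe the same event: same site, same timing and the same 4-hour threshold. They disagree on whether the injection must be given and on how much is given. Nothing else in the document says which prevails.

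The repeat is part of the experimental intervention, in children aged 1 to 18. The same child could receive different volumes, or no second injection, and each course would agree with one sentence of the protocol. A protocol deviation cannot be defined on that basis.

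The timing also matters for interpretation. The injection comes just before emergence, which Section 5.0 makes time zero, and from then on "all symptoms indicating nausea and/or vomiting and pain will be recorded". The treatment being evaluated in long operations is therefore not uniquely defined when outcome recording begins.

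**Working it through.** **Inputs, all from Section 5.0 unless noted.** Initial volume V = 3 to 5 ml. Rule 1 (general text): repeat of 2.5 to 3 ml, mandatory. Rule 2 (Group A paragraph): repeat of V/2, bracketed as 1.5 to 2.5 ml, optional. Concentration 0.25%, which is 2.5 mg/ml. Group size 20 (Section 4.0).

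**Step 1: reproduce the plan's own figure.** Half of 3 ml is 1.5 ml and half of 5 ml is 2.5 ml. This matches the bracketed range exactly, so Rule 2 does refer to the 3–5 ml Erb's point injection and its range is not a typing slip.

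**Step 2: can both volume rules be met?** Rule 1 needs a repeat of at least 2.5 ml. Under Rule 2 that means V/2 ≥ 2.5, so V ≥ 5. The plan caps V at 5 ml. The only joint solution is V = 5 ml with a repeat of 2.5 ml.

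**Step 3: size of the gap when a repeat is given.** Gap = (2.5 to 3) − V/2; percentage = gap ÷ (V/2); mg = gap × 2.5.

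| Initial V | Rule 2 repeat | Rule 1 repeat | Gap | Gap as % of Rule 2 repeat | Gap in mg |
|---|---|---|---|---|---|
| 3 ml | 1.5 ml | 2.5–3 ml | 1.0–1.5 ml | 67–100% | 2.5–3.75 |
| 4 ml | 2.0 ml | 2.5–3 ml | 0.5–1.0 ml | 25–50% | 1.25–2.5 |
| 5 ml | 2.5 ml | 2.5–3 ml | 0–0.5 ml | 0–20% | 0–1.25 |

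As a share of the total Erb's point volume (initial plus repeat), the gap is smaller:

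- V = 3 ml: 5.5–6 against 4.5 ml, or 22–33% more.
- V = 4 ml: 6.5–7 against 6 ml, or 8–17% more.
- V = 5 ml: 7.5–8 against 7.5 ml, or 0–7% more.

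**Step 4: size of the gap when the optional repeat is not given.** The gap is then the whole Rule 1 injection: 2.5 × 2.5 = 6.25 mg to 3 × 2.5 = 7.5 mg. If both sides are injected and the volume applies to each side (an assumption), it is 12.5 to 15 mg.

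**Step 5: children affected.** The plan gives no distribution of operating times, so only bounds are possible. If the optional sentence binds Group A alone, the range is 0 to 20. If it also governs Group C, it is 0 to 2 × 20 = 40.

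**Step 6: the 4-hour clock.** Rule 2 counts from the initial block. Rule 1 refers to the length of the procedure and names no starting point. This needs clarifying but is secondary to the conflict above.

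**The case against.** The strongest reply is that the conflict is narrow.

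- It arises only past 4 hours, and possibly in no child.
- Giving a repeat satisfies both the mandatory and the optional wording, so strict incompatibility is confined to volume, and only when the initial volume is below 5 ml.
- The 100% figure belongs to one corner (3 ml first, 3 ml repeated); against total volume the largest gap is 33%.
- The plan already allows a 2 ml spread in the initial injection, more than the 1.5 ml maximum gap per side.
- The Group A sentence might simply be the specific rule that overrides the general one.

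Much of this is fair as a limit on size: the number affected is unknown, the total-volume percentages are a legitimate second measure, and the literal layout points to Group A alone, hence at most 20 children.

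It does not remove the contradiction. A range that the plan permits differs from two instructions that exclude each other. Omitting the repeat is allowed by one sentence and breaches the other, even at 5 ml. The override reading is stated nowhere. It would also leave Group A with an optional half-volume repeat and Group C with a mandatory 2.5–3 ml one, so the block would differ between the two arms that share it. Nor is discretion implied: where the plan leaves re-dosing to the anaesthesiologist, as with ondansetron, it says so.

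**Conclusion.** The contradiction is real and must be resolved. For any initial volume below 5 ml, no repeat volume complies with both rules. At 5 ml the volumes meet only at 2.5 ml, and the mandatory-versus-optional conflict remains.

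The per-side figures assume that the stated volume applies to each injected side, which the plan does not say for the repeat. They double for bilateral blocks on that assumption.

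No claim is made about the effect on nausea or vomiting, and the sample size calculation is untouched. The point matters because it is a contradictory local anaesthetic instruction for children within the treatment under test.

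**What to change.** The clinical investigators should reconcile the two passages into one statement in Section 5.0 that settles four things:

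- the repeat volume;
- whether the repeat is required or optional;
- when the 4 hours start;
- whether and how the rule applies to Group C.

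The statement should also say how the volume applies when both sides are blocked. Which rule to adopt is a clinical decision, and no view is taken here.

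If the data collection sheets, which are not in the document, do not already record whether a repeat was given and its volume, that should be added.

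The cost is a wording amendment and at most one data field, with no extra patients or procedures.

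### Group C's nerve block is not uniquely defined: the allocation list and common procedure point to two injection sites, but the Group C paragraph names only one

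*Combined protocol and SAP*

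**What the plan says.** Section 4.0 (Enrollment/Randomization) lists the arms. The first is "Group A Nerve of Arnold block with superficial cervical plexus block (SCPB"), a two-site block. The third is "Group C Block + IV dexamethasone (Decadron + ondansetron (Zofran"), with no site given for the block.

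Section 5.0 (Study Procedures) introduces the block patients jointly: "For all patients randomized to receive regional nerve block (Group A & C) a time out before regional anesthesia will be performed". It then describes each injection in turn. It starts with the ear canal ("The nerve of Arnold block is located at junction of the ear tragus and external 1/3 of ear canal") and goes on to the superficial cervical plexus at Erb's point. Neither description is restricted to one group.

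The arm paragraphs follow. Group A's names both sites: "regional block at the Erb's point and Nerve of Arnold". Group C's names one: "a regional block at Erb's point (superficial cervical plexus block) and will receive an anti-emetic drug regiment".

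Section 2.0 gives the hypothesis: "We hypothesize another potential antiemetic mechanism by the blockade of the auricular branch of the Vagus nerve at the ear canal", used together with a block at superficial cervical plexus level.

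**The concern.** The two arm paragraphs are parallel instructions, and they do not match. A clinician working from the Group C paragraph would omit the ear-canal injection. One working from the allocation list and the common procedure would give it. Both could reasonably believe they were following the protocol.

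At stake is what one of the three randomised arms receives, and so what the comparisons with that arm mean. If practice varied between clinicians, Group C would be a mixture. The data items listed in Section 5.0 do not include the sites injected, so the mixture might not be recoverable at analysis. Section 7.0 allows a patient to be withdrawn for failure to comply with the protocol, yet compliance with the Group C block is itself undefined.

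**Working it through.** The point rests on comparing texts, so the places are set side by side.

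| Place | Group A block | Group C block |
|---|---|---|
| Section 4.0, list of groups | Nerve of Arnold + plexus | Block, no site named |
| Section 5.0, opening | Both sites described, A and C introduced together | Same text |
| Section 5.0, arm paragraphs | Erb's point + nerve of Arnold | Erb's point; nerve of Arnold not mentioned |
| Section 6.0 and the captions at the end | Blocks mentioned, no sites assigned to groups | Same |

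**Step 1. Is a two-site block for Group C stated?** No, only implied. In Section 4.0 the only block defined is the two-site one. The sentence in Section 5.0 that joins A and C concerns the time out.

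**Step 2. Is a one-site block for Group C stated?** Not explicitly. The Group C paragraph names one site but does not exclude the other. Where Section 5.0 does mean a restriction it says so, as for Group A's repeat injection: "may be repeated at Erb's point only with half the initial volume of local anesthetic". The Group C sentence begins by saying patients receive both, but its grammar is broken, and the word can as easily refer to block plus drugs.

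**Step 3. What each comparison estimates.**

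| Contrast | If C has two sites | If C has Erb's point alone |
|---|---|---|
| A vs B | Two-site block vs drugs | Unchanged |
| C vs B | Adding the two-site block to the drugs | Adding the plexus block alone to the drugs; still unconfounded |
| C vs A | Adding the drugs to the same block | Adding the drugs and dropping one injection |

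Two of the three contrasts change meaning.

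**Step 4. Patients concerned.** Planned enrolment is 3 × 20 = 60. On the literal reading up to 20 patients do not receive the ear-canal injection: 20/60 = 33% of those randomised, and 20/(20 + 20) = 50% of those assigned a block. On the two-site reading the number is 0.

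**Step 5. Does the sample size depend on this?** The inputs in Section 8.0 are 90% vs 50%, two-sided 5% and 80% power. With pooled variance and no continuity correction:

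n = [1.960 × √(2 × 0.7 × 0.3) + 0.842 × √(0.9 × 0.1 + 0.5 × 0.5)]² / 0.4² = (1.270 + 0.491)² / 0.16 ≈ 19.4, rounded up to 20 per group.

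This reproduces the plan's figure, and power at 20 per group is 0.813. No input refers to the block sites, so reconciling the text changes no stated number.

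**The case against.** The strongest reply is that this is an ambiguity rather than a contradiction, and that the protocol read as a whole favours two sites. The hypothesis pairs the ear-canal block with the plexus-level block, the common procedure gives both injections, and the garbled Group C sentence looks more like dropped words than a deliberately different block. That is fair, and a drafting slip is quite possible. But likelihood does not settle what an arm receives, and the Group C paragraph is the most specific text on it.

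Second, the time out requires the location of the block to be stated before injection. This helps at the bedside. It does not say which sites Group C should have, and it is not a research record.

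Third, the protocol never specifies C vs A or C vs B, and its stated aim of comparing established therapies with nerve blocks is closest to A vs B, which is unaffected. Both comparisons with C also remain valid randomised comparisons of whatever regimens were given. This stands: the harm is to interpretation, not to validity, error rate or power. Even so, Section 8.0 refers to a difference between all three groups and Section 5.0 plans a three-group cost comparison, and neither can be interpreted without knowing what Group C received.

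Finally, the protocol gives some antiemetic rationale for the plexus block by itself. Section 2.0 describes the Erb's point target as a vagal branch, and Section 1.0 cites reduced pain and opioid use. So even on the literal reading, Group C's block would not be without rationale.

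**Conclusion.** The concern holds and should be fixed before the plan is relied on. The intervention in one of the three arms is not uniquely defined, and nothing in the document resolves it. Depending on the reading, between 0 and 20 Group C patients would not receive the ear-canal injection, and two of the three pairwise contrasts would answer different questions.

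The upper figure assumes full enrolment of 20 in Group C and uniform literal compliance with its paragraph. These are counts of patients, not estimates of bias. That the text is inconsistent is certain; that Group C's block was meant to differ from Group A's is not claimed.

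**What to change.** Reconcile Section 4.0, the opening of Section 5.0 and the Group C paragraph. Define the injected sites once and have both the Group A and the Group C paragraphs refer to that definition. If the two blocks are meant to differ, say so in Section 4.0 and state what C vs A and C vs B then estimate. Which block Group C receives is for the sponsor to decide.

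Add a data-collection field for the sites actually injected in each patient, so that the treatment given in Group C can be reported.

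The cost is a wording amendment and one extra field, with no additional patients.
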